8.2 Randomization Scheme

None

8.3 Endpoint Assessment

8.3.1 Primary endpoint

The primary endpoint will be assessed in an observational nature through the frequency and characterization of site engagement with uCor data. The assessment will be made study-wide in addition to geographic regions. Site engagement will be assessed through the following:

- 8.3.1.1 The number of data updates received by the µCor subject management system.
- 8.3.1.2 An assessment of the approximate time spent reviewing data reports assessed within sites and across sites. Investigators will be asked, for each report, whether they spent 0-5min, 5-10min, or greater than 10 minutes reviewing the data.
- 8.3.1.3 The number of medication changes based on µCor data and the number of lifestyle modifications were recommended to the subject.
- 8.3.1.4 The number of medication changes based on symptoms reported by subjects or from subject incidental findings.
- 8.3.1.5 The number of times high µCor measurements were reduced below threshold levels after medication was titrated or lifestyle modifications were recommended.

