Unplanned visits to the physician office or hospital will be captured and defined as visits that the subject did not plan beyond 48 hours. In case of adverse skin reaction to the μ Cor adhesive and/or electrodes, on the discretion of physician, subjects may discontinue wearing the device for up to 48 hours. In the event the subject has stopped wearing the device completely, follow up phone calls will continue to be conducted per protocol in order to capture clinical information.

During the Day 90 visit, the subject will be given the option to continue wearing the μ Cor for an additional 90 days. Furthermore, if the subject experienced a heart failure related clinical event within the initial 90 days of wear, the subject will be given the option of wearing the μ Cor for 30 days following the heart failure event. If the subject chooses additional wear time, weekly phone calls and monthly visits will be structured identical to that of the main study period. The μ Cor will be returned at end of use.

Data updates will be delivered to the site when the day averaged TFI exceeds a threshold greater than three standard deviations of the baseline TFI level for three consecutive days. Upon receiving a device data update, the investigator will receive detailed information into how the device measurements have tracked over the days leading up to the notification. When receiving a data update, the site will be required to review the most recent report within 24 hours, and explain their reasoning whether they choose to contact the subject or not to contact the subject. The data review must occur prior to every scheduled subject contact.

When acting upon the data update, the site may contact the subject to assess the subject's current symptoms and history, and make an informed decision within the context of both device measurements and standard medical care as to what actions to take with the subject. Potential actions the site could take will include, a prescription drug change or titration, a request for an office visit, a request for hospitalization, and request for lifestyle or diet modifications. The site will document any changes to subject care within the case report forms. Unscheduled contacts that the subject initiates will be recorded as well.

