3.2 Primary Study Endpoints

The primary endpoint that will be evaluated at the end of the study includes:

3.2.1 Investigator Engagement: Investigator engagement will be assessed at the study site level as well as across all study sites.

Investigator engagement will be assessed through the number of data updates delivered by the μCor subject management system, the time spent reviewing each data report, the number of medication changes based on μCor data, the number of lifestyle modifications that are recommended to the subject, the number of medication changes based on symptoms reported by subjects or from subject incidental findings, and the number of times high μCor measurements are reduced below threshold levels after medication was titrated or lifestyle modifications were recommended.

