 - Any physician visits, both planned and unplanned
 - Any hospitalization, including heart failure hospitalization
 - Any emergency room visits
 - Any symptoms, including syncope, dyspnea, palpitations and chest pain
- 6.2.4.4 A weight measurement will be obtained.
- 6.2.4.5 Subjects will be given a physical assessment
- 6.2.2.6 Daily cardiac medications taken by the subject will be reviewed and compared to the last listed cardiac medications documented by the study. Any new cardiac medications or changes in medication will be recorded (i.e. dosage changes or new medications administered)
- 6.2.4.7 Subjects will be asked if they would like to continue wear for an additional 90 days. If the subject had experienced a heart failure related clinical event within the previous 90 days, the subject will also be given the option to continue wear for 30 days following the most recent heart failure event.

6.3 *Unscheduled Visits*

- 6.3.1 Clinic visits, ED visits, and hospitalizations that have resulted from a device data update will be defined as unscheduled events. Separately, all heart failure related contact with the subject either initiated by the subject or the site will be defined as an unscheduled visit. Heart failure contact includes, but is not limited to, contact with the subject concerning new or worsening heart failure symptoms such as dyspnea, pedal edema, and shortness of breath.
- 6.3.2 Upon receiving a data update, which will be initiated when the day averaged TFI readings have exceeded for three consecutive days a threshold defined by three standard deviations of baseline TFI, the site study team will reach out to the subject within 24 hours. The data update will be delivered to the site via either fax, email, or phone call.
- 6.3.3 The investigator will make a decision whether to contact the subject or take no further action based on the data update, and document the reason. There will be a structured interview between the investigator and subject. The investigator will have access to a report that displays the device data.
- 6.3.4 If the subject is called after device data update, the subject's symptoms and recent history will be documented, and a medical decision, within the context of standard of care,

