8.1 Sample Size

80 sites and 300 subjects will provide a reasonable estimate of site engagement with the device data. Three to five subjects per site will provide a reasonable estimate of site engagement per subject. We expect site variability in subject management. 80 study sites will be necessary to control for both site and regional differences in subject management.

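### Four of the five primary engagement components are counts with no stated exposure denominator or observation window, although wear time varies by design and results are read by site and region.

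*Combined protocol and SAP*

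**What the plan says.** Section 3.2 opens with "The primary endpoint that will be evaluated at the end of the study includes" and then lists the engagement measures. It adds "Investigator engagement will be assessed at the study site level as well as across all study sites". Section 8.3.1 has the same endpoint "assessed in an observational nature through the frequency and characterization of site engagement" and continues: "The assessment will be made study-wide in addition to geographic regions".

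Of the five items in 8.3.1, four are numbers of occurrences: data updates (8.3.1.1), device-based medication changes and lifestyle recommendations (8.3.1.3), symptom-based medication changes (8.3.1.4), and high readings brought back under threshold after an action (8.3.1.5). Review time (8.3.1.2) is a time band recorded for each report. Section 8.4 restates most of the counts as frequencies without giving a unit. It also adds one ratio, physician actions as a percentage of data updates.

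On exposure, 3.1.1 sets wear at up to 90 days and allows for subjects who stop sooner; their weekly calls continue but their visits do not. At day 90, "the subject will be given the option to continue wearing the" device for a further 90 days. Under 6.2.4.7, if there was a heart failure event, "the subject will also be given the option to continue wear for 30 days following the most recent heart failure event". Calls and visits in the extra period follow the same pattern as before. Section 7.1 has the sponsor track wear time from daily transmissions, for compliance purposes, and anticipates wear above 70%.

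**The concern.** A data update needs three consecutive days of averaged readings above threshold (3.1.1), so it can arise only while the device is worn. Device-based actions follow from updates or from the data reviews that accompany wear (6.2, 6.6). Returns below threshold need a reading to be seen at all. Longer wear therefore produces more of each, whatever the site's attentiveness.

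The results are to be read by site and by region, and 8.1 justifies 80 sites by the need to deal with site and regional differences in management. If one region's subjects extend more often, its totals will be higher and could be taken for greater engagement. With three to five subjects per site, one subject's choice can move a site's total noticeably. Because the endpoint is purely descriptive, the unit in which it is described carries the whole primary result. If that unit is chosen after the data are seen, the choice can shape the finding.

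**Working it through.** **1. The plan's own figure.** Section 8.1 states "80 sites and 300 subjects will provide a reasonable estimate of site engagement with the device data" and "Three to five subjects per site will provide a reasonable estimate of site engagement per subject". 300 / 80 = 3.75 subjects per site, which lies within 3 to 5 (80 × 3 = 240; 80 × 5 = 400). The figures agree with each other. No rate, precision target or power is given, so nothing further can be reproduced.

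**2. Model.** Expected count = daily rate × days at risk. The daily rate stands for engagement and is held equal throughout. The documents give neither a rate nor an extension uptake, so uptake below is assumed and varied.

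**3. One subject.** Full extension against none: 180 / 90 = 2.0.

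**4. One site of four subjects.** If one extends: (3 × 90 + 180) / (4 × 90) = 450 / 360 = 1.25.

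**5. Two regions of equal size.** With a share f taking the extra 90 days, mean wear is 90(1 + f), so the count ratio is (1 + fB) / (1 + fA).

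| Uptake A | Uptake B | Count ratio | Ratio per wear-day |
|---|---|---|---|
| 0% | 25% | 1.25 | 1.00 |
| 20% | 60% | 1.6 / 1.2 = 1.33 | 1.00 |
| 10% | 50% | 1.5 / 1.1 = 1.36 | 1.00 |
| 0% | 50% | 1.50 | 1.00 |
| 0% | 100% | 2.00 | 1.00 |

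**6. Would noise hide it?** Poisson counts were simulated for two regions of 150 subjects with equal rates and uptake of 20% v 60%. A nominal two-sided 5% comparison of raw counts flagged a difference in 83%, 97% and over 99% of runs, at assumed rates of one occurrence per 90, 45 and 30 wear-days. Per wear-day it did so in about 5%. The plan specifies no such test; this only shows that the distortion would be visible above sampling variation.

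**7. Event-linked option.** Read as wear until 30 days after the latest event on day T, the added time is max(0, T + 30 − 90). The most is 30 days, a ratio of 120 / 90 = 1.33. If T is uniform over days 0 to 90 (assumption), time is added only when T exceeds 60, that is in one third of cases, by 15 days on average among those. The mean is 15 / 3 = 5 days. The 90-day option drives volume; the event-linked option is small but ties exposure to outcome.

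**8. Which exposure belongs to which item.**

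| Item | Days or occasions at risk |
|---|---|
| 8.3.1.1 updates | wear-days |
| 8.3.1.2 review time | already per report |
| 8.3.1.3 device-based actions | updates, or reports reviewed (6.6 allows action without an update) |
| 8.3.1.4 symptom-based changes | follow-up time, since calls continue after wear stops |
| 8.3.1.5 returns below threshold | updates followed by an action |

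**The case against.** The best reply is that *frequency* may mean a rate. Section 8.3.1 uses the word in its opening sentence, 8.4 uses it for most of the counts, and 8.1 speaks of engagement per subject. That stands in part: a rate is not excluded. But the list in 8.3.1 consists of numbers, and neither section states a unit or a window.

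A second reply is that 8.4 already has a sound ratio, actions as a percentage of updates, which longer wear does not mechanically inflate. That is right, and it covers much of 8.3.1.3. It does not cover the update counts, the symptom-based changes, or actions arising from weekly reviews without an update.

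Third, the analysis is descriptive, with no test or error rate at stake, and wear time is recorded, so rates can be derived later. This limits the harm but leaves the choice of unit until after the data are seen.

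Fourth, a rate per wear-day already corrects for unequal wear, so a day-90 window may seem a mere preference. The rate corrects for the amount of exposure, not for who supplies it. Subjects who extend are self-selected, and a common window avoids mixing their later experience into the main comparison. The documents do not show that rates differ in the extension.

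Some stronger readings are tempting but unsupported:

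- **That the plan prescribes pooling extension data.** Evaluation at the end of the study says when, not which days; 3.1.1 and 6.2 both distinguish the extra wear. The documents are silent.
- **That sites and regions cannot be compared.** This is true of unadjusted counts only, not of the data.
- **That comparisons between subjects are distorted.** None is planned.
- **That counts would differ several-fold between sites.** This needs whole sites of full extenders set against whole sites of early stoppers, at wear durations the documents do not give.
- **That event-linked wear drives the problem.** It adds at most about 30 days.

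**Conclusion.** The point holds for 8.3.1.1, 8.3.1.3, 8.3.1.4 and 8.3.1.5, and not for review time per report or for the action percentage. Tabulated as listed, the four count items confound engagement with time at risk. The size is a factor of 2 for a subject who extends fully, and 1.25 to 1.50 between regions over the partial uptakes shown (1.33 for 20% v 60%). These ratios assume a constant daily rate, otherwise complete wear, and uptake figures that the documents do not supply. For 8.3.1.4 the relevant exposure is follow-up time rather than wear, so early stopping of wear alone need not reduce it. Early stopping, partial wear and unequal numbers of subjects per site also make exposure uneven, so the extension is not the only source. The change should be made: it goes beyond wording, since rates are a better method than the listed counts, but the data themselves are not compromised.

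**What to change.** In 8.3.1 and 8.4:

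- Report data updates per 100 device wear-days, with wear-days taken from the daily transmissions described in 7.1.
- Report device-based medication changes and lifestyle recommendations per data update or per report reviewed, keeping actions after updates separate from actions arising from weekly reviews.
- Report returns below threshold per update that was followed by an action.
- Report symptom-based medication changes (8.3.1.4) per subject follow-up time.
- State that the main window is days 0 to 90, and show the extension period in a separate table.
- Tabulate the number of subjects and wear-days by site and region beside the engagement measures.

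The cost is a wording change and some extra tables. Wear time is already captured, and 3.1.1, 6.3 and 6.6 already require sites to document actions; the forms need only record whether an action followed an update or a weekly review. The small downside is that extension data leave the main table.

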3.1 General Design

3.1.1 Study Description

Subjects meeting the inclusion/exclusion criteria will wear μ Cor for up to 90 days from the day of fitting. 300 total patients will be enrolled. Subjects will be fitted with μ Cor during discharge of a heart failure related hospitalization or within a clinic visit that has occurred within 10 days of a heart failure related hospitalization. The μ Cor fitting will mark day 0 of the study. An LVEF measurement will be recorded during enrollment or within 30 days post enrollment if an LVEF measurement has not been recorded within 30 days prior to enrollment. Any LVEF will qualify for the study. An investigator assessment will be performed during all clinic visits. The assessment template is shown in Appendix A.

Subjects will be given a diary at enrollment that will ask them to rate their degree of specific symptoms of heart failure such as shortness of breath and fatigue as well as mark any heart failure related clinical events or medication changes that have occurred since the last entry. The subject diary is shown in Appendix A.

Phone calls will be based on weekly data reviews or data updates. A review of the data will be conducted by the site before the weekly phone call and the most recent (Transthoracic Fluid Index) TFI will be recorded. The subject will receive a study based weekly phone call asking the subject about any recent heart failure related clinical events or change in heart failure symptoms. The weekly phone calls will continue if the subject has stopped wearing the device. During the weekly phone call the subject will be reminded to fill out the daily diary. No phone calls will be given on the week where there is a study follow up visit.

A review of the data will be conducted by the site before the office visit and the most recent TFI will be recorded. Study face to face follow up visits will occur at day 30, day 60, and day 90. There will be no follow up visit if the subject has stopped wearing the device. During follow up visits the subjects will be asked about any heart failure related clinical events or change in symptoms that have occurred since the last follow up.

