8.4 Statistical Methods

Concerning the primary endpoint, investigator engagement will be assessed through the number of data updates delivered by the µCor subject management system, frequency of medication changes based on µCor data, frequency of lifestyle modifications that are recommended to the subject, frequency of medication changes based on symptoms reported by subjects or from subject incidental findings, and frequency high µCor measurements that are reduced below threshold levels after medication was titrated or lifestyle modifications were recommended.

Concerning the secondary endpoints, associations between µCor measurements and clinically related heart failure events will be assessed through sensitivity/specificity analyses. µCor measurements at both baseline (first day of fitting) and the time of heart failure admission will be compared among subjects with or without heart failure related events using t-tests or other appropriate statistical methods.

For primary, secondary, and safety endpoints, descriptive statistics and qualitative analysis will be performed as appropriate. Descriptive statistics will include frequency of data updates delivered by the µCor data system, frequency of physician action to µCor data or µCor data updates, and physician action events as a percentage of all data updates received.

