8.6.3 Handling missing data

8.6.3.1 Missing data will not be replaced by any algorithm.

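### The review-time item in 8.3.1.2 overlaps at 5 minutes and has no 'not reviewed' answer, so on its own it cannot separate non-review from a short review

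*Combined protocol and SAP*

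**What the plan says.** Section 2.1 has a single primary objective, investigator engagement with the device data. Section 3.2.1 lists its components, among them "the time spent reviewing each data report". Section 8.3.1.2 describes this component as "An assessment of the approximate time spent reviewing data reports assessed within sites and across sites", and has investigators state, for each report, "whether they spent 0-5min, 5-10min, or greater than 10 minutes reviewing the data". No fourth answer is listed. Neither 8.3.1.2 nor the missing-data text in 8.6 says how to record a report that was never opened. The form itself is not in the documents; Appendix A shows only the congestion survey and the subject diary.

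The plan also creates other traces of review:

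- Section 3.1.1: "A review of the data will be conducted by the site before the weekly phone call and the most recent" TFI value is noted. The same applies before office visits.
- Section 3.1.1: "The data review must occur prior to every scheduled subject contact".
- Section 3.1.1, after a data update: "the site will be required to review the most recent report within 24 hours, and explain their reasoning" for contacting the subject or not. Section 6.3.3 also asks for the reason to be documented.
- Section 8.4 reports "physician action events as a percentage of all data updates received".

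Two further points bear on the analysis. The list of primary measures that opens 8.4 leaves review time out, so only the general promise of descriptive statistics covers it. Section 8.6.3 states: "Missing data will not be replaced by any algorithm".

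**The concern.** An engagement endpoint should show whether sites looked at the data they were sent. Of the components listed in 8.3.1, review time is the only one that bears on this directly. The number of data updates is driven by the TFI threshold, so it reflects the device and the patient. Medication changes, lifestyle advice and returns below threshold record action or its result. A careful review that ends in no action leaves no trace in those counts, and neither does an unread report.

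The mandate to review does not make the question redundant, because whether sites comply is part of what the study sets out to describe. If the review-time item merges no review with brief review, the primary table cannot state from it how many reports were looked at. The shared boundary at 5 minutes is a smaller matter, but 5 is a natural rounded answer and sites may code it differently.

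**Working it through.** The plan gives no figure to reproduce here. The check is whether each possible review time has exactly one answer, and what can then be learned from the counts.

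**Step 1: assign test times.** Inputs: the three categories in 8.3.1.2, read literally, and the exclusive set proposed below.

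| Review time (min) | Categories as written | Exclusive categories |
|---|---|---|
| 0 | 0 to 5 | not reviewed |
| 1 | 0 to 5 | under 5 |
| 4.9 | 0 to 5 | under 5 |
| 5 | 0 to 5 **and** 5 to 10 | 5 to 10 |
| 7 | 5 to 10 | 5 to 10 |
| 10 | 5 to 10 | 5 to 10 |
| 10.1 | over 10 | over 10 |

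The overlap is at 5 minutes only. Ten minutes has one category as written, because the top answer starts above 10. Zero shares a category with 1 and 4.9 minutes.

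**Step 2: what the counts identify.** Let N be the number of reports issued, *a*, *b* and *c* the counts in the low, middle and top categories, and *m* the blanks, so N = *a* + *b* + *c* + *m*. Taking answers at face value, *b* and *c* are reviewed reports. An unread report can only sit in *a* (zero is inside the range) or in *m* (left unanswered). From this item alone, the not-reviewed share lies between

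- lower bound: 0
- upper bound: (*a* + *m*)/N.

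With no blanks, the range runs from 0 to the observed share of the lowest category. The documents give no value for *a* or *m*, so this cannot be turned into a number.

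With a separate 'not reviewed' count *n0*, the range becomes *n0*/N to (*n0* + *m*)/N. Its width is then *m*/N, the blank rate, instead of (*a* + *m*)/N.

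**Step 3: the boundary.** If *k* answers are exactly 5 minutes, the share of the lowest category can move by up to *k*/N according to how sites choose. The documents give no *k*.

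**Step 4: can the other records fill the gap?**

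| Record | Applies to | Limit as a measure of non-review |
|---|---|---|
| TFI logged before contact (3.1.1) | weekly calls and visits | a missing value suggests non-review; not listed as a measure in 8.3.1 or 8.4 |
| Reason for contact or no contact (3.1.1, 6.3.3) | data updates | does not cover routine weekly reports; not listed as a measure |
| Actions as a percentage of updates (8.4) | data updates | a genuine review may end in no action (6.3.4), so a low figure is ambiguous |
| Blank review-time answer | every report | not replaced (8.6.3), and no rule says what a blank means |

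Each record could raise a suspicion of non-review. None is planned as a count of it.

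**The case against.** The strongest reply is that non-review is not invisible in this study. A missing TFI entry before a call, or a missing reason after a data update, would show up in the data. This stands. A reader might infer from the review-time item that non-engagement cannot be seen anywhere in the primary endpoint. The documents do not support that, because the records required by 3.1.1 and 6.3.3 are indirect evidence. What remains is that the plan does not say they will be analysed for this purpose.

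Second, the question asks how long was spent reviewing, which presupposes a review. An unopened report might be left blank instead of being entered in the lowest category. This also stands: the coding of unread reports is inferred from the lower limit of zero and the lack of another answer. It does not remove the problem. A blank could equally be a forgotten item, and percentages among answered reports would then leave the unread ones out.

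Third, the measure is called approximate, is descriptive, and carries no test or success threshold. That is a fair reason to treat the overlap at 5 minutes as minor. Distortion between sites is possible but not shown.

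Fourth, a reader might put a size on the problem by assuming what share of reports goes unread, or by counting reports: 90/7 gives 12 full weeks, and 12 x 300 = 3,600 weekly reports. Neither shows the size. The documents give no share of unread reports. The count assumes full wear in every subject, although wear is up to 90 days with optional extension. It also says how many answers pass through the item, not how many are wrong.

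**Conclusion.** The point holds in a limited form. As written, the review-time item assigns 5 minutes to two answers and gives non-review no answer of its own, so this item cannot separate a report that was not opened from one reviewed briefly. Both facts follow from the wording of 8.3.1.2 and need no assumption. That unread reports would be entered in the lowest category is an inference; if they were left blank, the ambiguity would move to the blanks.

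The size is unknown. The not-reviewed share is bounded only by the combined share of lowest-category and blank answers, and the documents say nothing about either. The sample size is unaffected and no hypothesis test depends on the item. This is a cheap improvement to what the primary endpoint can show, not a threat to the study.

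**What to change.** In 8.3.1.2 and on the matching form item, replace the three answers with four exclusive ones: not reviewed; reviewed, under 5 minutes; 5 to 10 minutes; more than 10 minutes. This keeps the existing upper cut-point, which has no overlap. In the primary engagement table, report the not-reviewed share as its own line, with all reports issued as the denominator and blank answers counted separately. Add review time to the list of primary measures in 8.4 so that its analysis is named.

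The cost is one form item, one table row and a short text change. There are two small downsides. Any answers already collected in the lowest category cannot be divided afterwards and must be shown separately. And because the protocol requires review, 'not reviewed' amounts to reporting non-adherence and may be under-reported, so the line should be read as a minimum.
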